8.2.3. Safety Analyses

8.2.3.1. Safety Endpoints (including Primary Joint Safety Endpoint)

1. Joint Safety Endpoints.

The primary joint safety endpoint is the incidence of subjects with any of the adjudication outcomes of rapidly progressive osteoarthritis (type-1 or type-2), subchondral insufficiency fracture, primary osteonecrosis, or pathological fracture.

The primary endpoint will be shown by number of subjects treated and subject years of exposure (treatment plus follow-up periods), for individual treatment groups and differences between tanezumab treatment groups and the NSAID treatment group. The risk ratio and risk difference (using number of subjects as the denominator and then exposure as the denominator) with 95% confidence intervals will be calculated for the comparisons of each tanezumab treatment group versus the NSAID treatment group, as well as significance tests for each treatment comparison. The time to each event will be summarized, and (where there are sufficient numbers of subjects) Kaplan-Meier estimates of the time to event will be produced, together with an analysis of each tanezumab treatment group versus the NSAID treatment group using the log-rank test.

09001776e193181b6561Approved\Approved On: 08-10-2019 08:56 (GMT)

The primary analysis of the primary joint safety endpoint is the analysis of the exposure-adjusted risk difference. The analyses of the exposure-adjusted risk ratio, and risk difference and ratio based on percentage of subjects with the event will be secondary analyses.

The summary and analysis of the secondary joint safety endpoints will follow the same method described above for the primary joint safety endpoint.

2. Neuropathy Impairment Score.

The change from Baseline in the NIS for Weeks 2, 4, 8, 16, 24, 32, 40, 48, 56, 64 and 80 will be analyzed using a CMH test (stratified by the levels of the stratification factors) with change categories. Missing data will be imputed using LOCF only. For this analysis, Baseline data will not be carried forward in the case of a post-Baseline observation not being available for use in LOCF. An additional analysis will use the change from Baseline to the largest (worst) post-Baseline value and to the last value (summary, not analysis).

3. Radiographic Endpoints.

The change from Baseline to Weeks 56 and 80 in the Minimum Joint Space Width (JSW) for subjects with Kellgren-Lawrence grades of 2 or 3 in the index joint will be analyzed for subjects with measurements in the knee and hip separately. The analysis will also be performed for subjects with a Kellgren-Lawrence grade of 3 in the index knee. For subjects with an index joint of a knee, where both medial and lateral measurements are collected, if the baseline medial JSW is \leq the baseline lateral JSW, the medial view will be followed through the study for these analyses. If the baseline lateral JSW $<$ the baseline medial JSW, the lateral view will be followed through the study for these analyses. The percentage of subjects with narrowing over certain intervals will be shown, in addition to summary statistics of the mean (with standard deviation) and median change from Baseline.

Significant progression of osteoarthritis will be defined using the Bland-Altman method, as proposed by OARSI-OMERACT. Progression will be defined as 1.96 times the within-subject standard deviation of the change in JSW. The incidence of subjects with JSW narrowing greater than or equal to these values will be shown (with Kellgren-Lawrence grades of 2 or 3 in the index joint, and separately with Kellgren-Lawrence grade of 3 in the index knee), and incidence analyzed using logistic regression for binary data, taking into account Baseline JSW as a covariate.

The Radiographic endpoint summaries and analyses will be performed separately for subjects with osteoarthritis of the hip and knee. These analyses will use the Week 56 End of Treatment/Early Termination data and then Week 80 End of Study/Early Termination Visit 3 regardless of the study day of assessment and/or where subjects have discontinued early from the study. In the event of missing data, baseline data will not be carried forward for Radiographic data. Additional analyses will be performed for assessments at Week 56 and Week 80 (equivalent to observed data analysis for subjects who reach these time points), subject to a window of ± 4 weeks and ± 6 weeks for the Week 56 and Week 80 analyses respectively.

0900177e4193181b6561Approved\Approved On: 08-10-2019 08:56 (GMT)

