## 6.4.2. Procedures for Subjects Undergoing Joint Replacement

Subjects who have undergone or plan to undergo total joint replacement or other arthroplasty procedure during the study will be discontinued from investigational product.

Subjects who undergo total knee, hip or shoulder joint replacement surgery during the study (Double-blind Treatment Period or Follow-up Period) will be followed for 24 weeks after the procedure as part of a separate protocol (Study A4091064), provided the subject consents.

Transition procedures into Study A4091064 are determined by the timing of total joint replacement surgery:

- Subjects who have undergone or plan an immediate total knee, hip or shoulder joint replacement will be discontinued from the Double-Blind Treatment period and enter into the total joint replacement follow-up protocol (Study A4091064). At the discontinuation visit, all procedures scheduled for the Week 56 and Week 64 visits should be completed unless the Subject has already completed the Week 56 and Week 64 visits, in which case only Week 80 procedures will be required. In addition, if the Week 56 visit was not completed prior to termination, a general physical examination, body weight, WPAI:OA, EQ-5D-5L, TSQM v.II and mPRTI will also be obtained. Applicable Study A4091064 Baseline Visit activities should be completed on the same day as the Study A4091058 End of Treatment Visit.
- Subjects who plan to undergo total knee, hip or shoulder joint replacement during the study will be discontinued from the Double-blind Treatment Period and entered into Early Termination Follow-up (See Section 6.4) until their joint replacement procedure. For these subjects, a complete early termination visit should be conducted prior to the total joint replacement (See Section 6.4) and entrance into Study A4091064. Study A4091064 Baseline Visit activities should be completed on the same day as the Study A4091058 early termination visit. Subjects who have not undergone or scheduled total joint replacement surgery within the investigational product or safety follow-up period of this study will not be eligible for Study A4091064.

Subjects who undergo other types of joint replacement surgery or arthroplasty during the study should be discontinued from investigational product and complete the protocol specified Safety Follow-up Period, but not be entered into Study A4091064 for follow-up.

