### 9.1. Sample Size Determination

A sample size of approximately 1000 subjects for each of the treatment groups of NSAID, tanezumab 2.5 mg and tanezumab 5 mg will be used in this study. This sample size allows for a high probability of observing subjects with any component of the composite endpoint where the event rate over this study is very small. If the event rate were 0.25%, then there would be a >90% probability of observing at least one subject with an event in any single treatment group.

In addition, the sample size allows for good precision to estimate the incidence rate for each treatment group in order to estimate an upper bound for the true incidence rate. The table below gives the width of the 95% confidence intervals for the individual treatment groups with this sample size.

Observed Rate of Rapidly Progressive Osteoarthritis Type 2	95% Confidence Interval for Individual Treatment Groups (N=1000)
0%	[0, 0.37%]
0.1%	[0.00, 0.56%]
0.2%	[0.02, 0.72%]
0.3%	[0.06, 0.87%]
0.4%	[0.11, 1.02%]
0.5%	[0.16, 1.16%]
1.0%	[0.48, 1.83%]

Table IV. Estimated Event Incidence Kate Precision	Table 10.	Estimated Event Incidence Rate Precision
--	-----------	---

For the assessment of the incidence of subjects with a total joint replacement, a sample size of approximately 1000 subjects per group would be sufficient to demonstrate a significant difference ( $p \le 0.05$ ) between any two treatment groups, for a difference of 2% with an observed control group rate for total joint replacement of 2%. Similarly, for the assessment of the incidence of subjects with an adjudication outcome of rapidly progressive osteoarthritis type 2, a sample size of approximately 1000 subjects per group would be sufficient to demonstrate a significant difference ( $p \le 0.10$ ) between any two treatment groups, for a difference of 1% with an observed control group rate for rapidly progressive osteoarthritis of 0%.

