#### 9.2. Primary Analysis

### 9.2.1. Analysis of Primary Endpoints

The incidence of subjects with any of the adjudication outcomes of rapidly progressive osteoarthritis (type-1 or type-2), subchondral insufficiency fracture (or SPONK), primary osteonecrosis, or pathological fracture (primary composite endpoint) will be shown by number of subjects treated and subject years of exposure (treatment plus follow-up periods), for individual treatment groups and differences between tanezumab treatment groups and the NSAID treatment group. The risk ratio and risk difference with 95% confidence intervals will be calculated for the comparisons of each tanezumab treatment group versus the NSAID treatment group, as well as significance tests for each treatment comparison. The time to each event will be summarized, and (where there are sufficient numbers of subjects) Kaplan-Meier estimates of the time to event will be produced, together with an analysis of each tanezumab treatment group using the log-rank test.

The primary safety and efficacy population will be the ITT population, defined as all randomized subjects who received SC investigational product (either tanezumab or matching placebo). The primary efficacy analysis will use multiple imputation methods for missing data at Week 16. Details of the multiple imputation procedure are given below. All treatment comparisons will use the two-sided 5% significance level.

The co-primary efficacy endpoints will be analyzed using an ANCOVA model, with model terms for Baseline score, Baseline Diary Average Pain, index joint (hip or knee), Kellgren-Lawrence grade, NSAID cohort (diclofenac, celecoxib or naproxen) and treatment group, and study site as a random effect. The assessment of significance for the tanezumab SC versus NSAID treatment contrasts of the primary efficacy parameters will use a step-down testing strategy within each of the co-primary efficacy endpoints. This order of significance testing is defined as first testing tanezumab 5 mg versus NSAID, and if statistically significant ( $p \le 0.05$ ) to then test tanezumab 2.5 mg versus NSAID. Finally, the tanezumab dose group is declared as superior to NSAID if the corresponding treatment contrast is significant over all three co-primary endpoints (*two co-primary efficacy endpoints in Japan*). This testing procedure will maintain the Type I error to 5% or less within each of the co-primary efficacy endpoints (*two co-primary efficacy endpoints in Japan*).

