- *Incidence of subjects with progression of osteoarthritis in the index hip according to Bland and Altman method, at Week 56 and Week 80 (separately) (for subjects with Kellgren-Lawrence Grade 2 or 3 osteoarthritis of the index hip).*

The Bland-Altman method for defining progression of Joint Space Width (JSW), is to calculate the t-statistic (based on the number of subjects in the sample for the 0.975 percentile of the t-distribution) multiplied by the standard deviation of the change from Baseline to Week 56 and to Week 80 (two separate values, giving two different definitions of progression for each joint). These values represent the limit of the 95% confidence interval (CI) for a change of 0 over these time points. Note, 95% CI for the observed mean change is

09001776e193181b656ApprovedApproved On: 08-10-2019 08:56 (GMT)

not used because this would be affected by any treatment effect seen in the trial, that this endpoint is aiming to explore, and would be potentially biased. The lower bounds of the 95% CI for change from Baseline to Week 56 and to Week 80 would represent the definitions of progression of Osteoarthritis (OA) for Hip and Knee OA separately. The incidence of subjects with a reduction in JSW will then be compared according to the appropriate definition (Week 56 or Week 80; Hip or Knee). The calculation of the progression of OA definition and analysis of incidence will be performed separately for Weeks 56 and 80 and subjects with OA of the Hip and Knee, for the subset of subjects with Kellgren-Lawrence grade 2 or 3 and with just grade 3 (knee).

The adverse events of Abnormal Peripheral Sensation (APS) are defined in the table below.

Allodynia	Neuralgia
Axonal neuropathy	Neuritis
Burning sensation	Neuropathy peripheral
Decreased Vibratory Sense	Paraesthesia
Demyelinating polyneuropathy	Paraesthesia oral
Dysaesthesia	Peripheral sensorimotor neuropathy
Formication	Peripheral sensory neuropathy
Hyperaesthesia	Polyneuropathy
Hyperpathia	Polyneuropathy chronic
Hypoesthesia	Sensory disturbance
Hypoesthesia oral	Sensory loss
Intercostal neuralgia	Thermohypoesthesia
Sciatica	Carpal tunnel syndrome
	Tarsal tunnel syndrome

0900177649318166561Approved\Approved On: 03-10-2019 08:56 (GMT)

Adverse Events of the Sympathetic Nervous System are defined in the table below.

Abdominal discomfort	Micturition urgency
Anhidrosis	Nausea
Blood pressure orthostatic decreased	Nocturia
Bradycardia	Orthostatic hypotension
Diarrhoea	Presyncope

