Incidence of secondary composite endpoint, individual adjudication joint safety endpoints (RPOA-1, RPOA-2, RPOA-1/2, SIF, Primary ON, Pathological fracture), TJR, and TJR and any adjudication outcome	ITT	Exact analyses for risk difference and ratio (percentage)	Treatment group	Observed	Secondary Joint Safety Analyses
Time to joint safety event (Primary Composite, Secondary Composite, Individual Adjudication Events, TJR, TJR and any adjudication outcome)	ITT	Log-Rank (with KM estimates)	Treatment Group	Observed	Secondary Joint Safety Analyses
Incidence of Bland-Altman defined progression of OA for subjects with OA of the Hip (KL2,3) at Weeks 56/ET and 80/ET, and Weeks 56 and 80 (based on window)	ITT	Logistic Regression	BL JSW, Treatment Group	Observed	Radiographic safety endpoint
Incidence of Bland-Altman defined progression of OA for subjects with OA of the Knee (KL2,3) at Weeks 56/ET and 80/ET, and Weeks 56 and 80 (based on window)	ITT	Logistic Regression	BL JSW, Treatment Group	Observed	Radiographic safety endpoint
Change from Baseline in JSW for subjects with OA of the Hip (KL 2, 3) at Weeks 56/ET and 80/ET, and Weeks 56 and 80 (based on window)	ITT	ANCOVA	BL JSW, Treatment Group (Study site as a random effect)	Observed	Radiographic safety endpoint
Change from Baseline in JSW for subjects with OA of the Knee (KL 2, 3) at Weeks 56/ET and 80/ET, and Weeks 56 and 80 (based on window)	ITT	ANCOVA	BL JSW, Treatment Group (Study site as a random effect)	Observed	Radiographic safety endpoint
Change from baseline to Weeks 2, 4, 8, 16, 24, 32, 40, 48, 56, 64 and 80 in the NIS score, and Change from Baseline to Worst post-Baseline NIS score	ITT	CMH test	Treatment Group [1]	LOCF (Weeks 2, 4, 8, 16, 24, 32, 40, 48, 56, 64, 80), Worst post-baseline score	Safety Analysis
Survey of Autonomic Symptoms (SAS), number of symptoms and total impact score (by visit and change from Baseline)	ITT	Summary	NA	Observed	Safety Analysis

[1] CMH test will be stratified by the levels of the combined stratification parameters (18 levels). If there are <15 subjects in any combined stratification level then the CMH test will be unstratified.

09001776e49378b656\Approved\Approved On: 08-10-2019 08:56 (GMT)

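### The radiographic progression analysis has no rule for a replaced index joint, so it can leave out structural failures; the documents do not fix the size of the resulting bias

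*SAP*

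**What the plan says.** SAP 8.2.3.1 item 3 limits the radiographic set to index joints of Kellgren-Lawrence (KL) grade 2 or 3, with knee and hip analysed separately. Its threshold reads "Progression will be defined as 1.96 times the within-subject standard deviation of the change in JSW". Incidence beyond the threshold goes into a logistic regression with baseline JSW as covariate. SAP 6.2 builds the threshold from a t quantile times the standard deviation of the change from baseline, and explains it thus: "These values represent the limit of the 95% confidence interval (CI) for a change of 0 over these time points".

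The main analyses take the Week 56/ET film and then the Week 80/ET Visit 3 film, whatever the study day. On absent films the section says "In the event of missing data, baseline data will not be carried forward for Radiographic data". Additional analyses keep only films within 4 weeks of Week 56 or 6 weeks of Week 80. The SAP 8.2.5 row "Incidence of Bland-Altman defined progression of OA for subjects with OA of the Hip (KL2,3) at Weeks 56/ET and 80/ET" gives its missing-data handling as observed, and the knee row is the same. Joint replacement is not mentioned in item 3.

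Protocol 6.4.2 states "Subjects who have undergone or plan an immediate total knee, hip or shoulder joint replacement will be discontinued from the Double-Blind Treatment period". Subjects planning later surgery have a complete early termination visit beforehand. Consenting subjects then move to a separate follow-up study. Protocol 6.4.1 asks for films on withdrawal only if at least 30 days have passed since the last set.

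For scale, Protocol 9.1 has "A sample size of approximately 1000 subjects for each of the treatment groups of NSAID, tanezumab 2.5 mg and tanezumab 5 mg" and describes what this could show for replacement: "for a difference of 2% with an observed control group rate for total joint replacement of 2" per cent.

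**The concern.** A replaced joint has no native joint space left to measure. Under an observed-data analysis it leaves both numerator and denominator, or is scored on a film taken before the joint failed. The absence is then caused by the outcome of interest. If one arm has more replacements, it also loses more of its worst joints, and the comparison moves towards no difference on a joint-safety endpoint.

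The issue is foreseeable here. Protocol 1.2.3.4.1 describes rapidly progressive osteoarthritis (RPOA) through rapid joint space narrowing, and Protocol 1.2.3.2 reports a higher risk of it with tanezumab than with placebo or active comparator. For efficacy, SAP 7 deliberately imputes a poor value after discontinuation for death, adverse event or lack of efficacy. The structural endpoint has no counterpart.

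**Working it through.** **Step 1. Which replaced index joints still have a film.**

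- Planned surgery: the pre-surgery termination visit includes the Week 80 procedures, hence radiographs. The joint can contribute to Week 56/ET. The SAP does not say whether this film may also stand as Week 80/ET Visit 3.
- Surgery already done: the discontinuation visit follows surgery, so no native joint space can be read.
- Films within the previous 30 days: no withdrawal film is required. The SAP does not say whether an earlier scheduled film may serve instead.
- Week 80/ET Visit 3: this visit falls 24 weeks after the last injection. Most replaced subjects will by then have a prosthesis or be in the follow-up study.
- Windowed analyses: a subject who leaves before the window contributes nothing.

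The loss is therefore partial at Week 56/ET and heavier elsewhere.

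**Step 2. The protocol's own figure.** 20/1000 v 40/1000 gives p = 0.012 (Fisher) and p = 0.009 (chi-square). The Protocol 9.1 statement of significance at 0.05 reproduces. It concerns replacement in any joint at any KL grade.

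**Step 3. Progression among measured joints.** The documents state no expected rate. Under the SAP 6.2 threshold with normal changes of mean zero, P(Z ≤ −1.96) = 2.5%. Mean narrowing of 0.1, 0.3 or 0.5 SD raises this to 3.1%, 4.8% or 7.2%.

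**Step 4. Size under the 2% v 4% scenario.** Let s be the share of replacements that are analysed KL 2-3 index joints without a usable film; the documents do not give s. With lost proportion u = s × replacement rate, counting lost joints as progressed gives u + (1 − u) × 2.5%. For s = 1: 0.02 + 0.98 × 0.025 = 4.45% and 0.04 + 0.96 × 0.025 = 6.40%.

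| s | Control | Other arm | Risk ratio | Odds ratio | Failures left out (control / other) |
|---|---|---|---|---|---|
| 0 | 2.50% | 2.50% | 1.00 | 1.00 | 0 / 0 |
| 0.25 | 2.99% | 3.48% | 1.16 | 1.17 | 17% / 29% |
| 0.5 | 3.48% | 4.45% | 1.28 | 1.29 | 29% / 45% |
| 1 (ceiling) | 4.45% | 6.40% | 1.44 | 1.47 | 45% / 62.5% |

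The observed-data analysis shows 2.5% v 2.5%, ratio 1.00, in every row. A higher measured rate shrinks the effect. At 4.8% and s = 1: 0.02 + 0.98 × 0.048 = 6.7% and 0.04 + 0.96 × 0.048 = 8.6%, risk ratio 1.28.

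**Step 5. Size under the protocol's historical rates.** Protocol Table 3 gives a composite that includes all-cause replacement. Take the comparator rate as the tanezumab rate minus 1/NNH, and s = 1.

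- 5 mg with risk mitigation: 4/1182 = 0.338%; 1/2506 = 0.040%; comparator 0.298%. Result 2.83% v 2.79%, odds ratio 1.01.
- Observed monotherapy: 23/4273 = 0.538%; 1/263 = 0.380%; comparator 0.158%. Result 3.02% v 2.65%, odds ratio 1.14.

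Table 3 pools studies of other durations, so these results are indicative.

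**The case against.** Four objections carry weight.

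1. A reader might infer that the trial expects replacements about as often as progression. The documents do not support this. The 2% and 4% describe what 1000 per group could detect, in any joint and any KL grade. The radiographic set excludes KL 4 index joints, and Protocol 1.2.3.4 says most RPOA cases had advanced disease in the affected joint. The same section reports comparable all-cause replacement across placebo, active comparator and tanezumab monotherapy. A difference between arms is a possibility, not the protocol's expectation. This stands, and it is why s = 1 is a ceiling.

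2. A reader might infer that every replaced joint is treated as missing. That is not written. Withdrawal films and pre-surgery visits are requested, and the main analysis uses ET films on any study day. This stands for much of Week 56/ET, but not for the gaps in step 1.

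3. The worst outcomes are counted elsewhere: adjudicated RPOA in the primary composite, and replacement as a secondary joint safety endpoint (SAP 6.2). This stands. The events are lost to this endpoint, not to the trial.

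4. Equating replacement with progression is an estimand choice. Protocol Appendix 14 allows adjudication as normal progression or as another diagnosis. This stands, and it argues against replacing the planned definition.

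Nor is the sentence barring baseline carry-forward a fault: it avoids imputing no change for a lost joint.

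**Conclusion.** The concern holds in a limited form. Item 3 is silent on replaced index joints and runs on observed JSW, so its incidence can omit structural failures. The comparison is biased towards no difference if replacement differs by arm. Early-termination films reduce the loss at Week 56/ET and do little at Week 80/ET Visit 3 or in the windowed analyses.

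The size depends on s and on the replacement rates, neither of which the documents settle. The 2% v 4% scenario gives risk ratios from 1.00 to a ceiling of 1.44; the historical rates give odds ratios of about 1.01 to 1.14 at most. Both rest on 2.5% progression among measured joints in each arm, which requires zero mean change and the SAP 6.2 threshold. SAP 8.2.3.1 words that threshold differently, and the two should be reconciled. Power for the ceiling contrast would be only 49% with 1000 per arm and 32% with 600, so the value lies in an honest estimate more than in a test.

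**What to change.** In SAP 8.2.3.1 item 3, pre-specify an additional progression-incidence analysis at Week 56 and at Week 80. It counts a KL 2-3 index joint as progressed if that joint was replaced, or adjudicated as RPOA, on or before the time point and has no later JSW. Show it beside the observed-data analysis, which stays as planned. Report by arm the number of replaced index joints with and without a usable post-baseline film, so that readers can see s directly. Add matching rows to SAP 8.2.5.

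The cost is SAP wording and a few table rows; the data are already collected. There are two downsides. A few joints replaced for pain without threshold narrowing would count as progressed, including some whose pre-surgery film shows no progression. The analysis also overlaps with the joint safety endpoints, and should be labelled accordingly.
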